# Previous and concomitant medications

#### Prohibited treatments:

VMAT2 inhibitors such as tetrabenazine, deutetrabenazine, or valbenazine are forbidden within 3 months prior to randomization and at any time during the whole study.

Neuroleptics indicated to treat chorea such as haloperidol, pimozide, or tiapride, and all other neuroleptics used off label as dopamine D2 receptor blockers to treat chorea are forbidden within 2 months prior to randomization and at any time during the whole study.

The following treatments are forbidden within 1 month prior to randomization and during the whole study:

- All monoamine oxidase (MAO) inhibitors.
- Levodopa and dopa-agonist drugs: apomorphin, ropinirole, pramipexole, rotigotine.
- Reserpine.
- Glutamate antagonists: amantadine, memantine, riluzole.
- Anti-arrhythmic drugs inducing bradycardia: diltiazem, verapamil, amiodarone, digitalis, quinidine, sotalol, disopyramide.
- Any other beta blocker antihypertensive medication.
- Central antihypertensive treatments: clonidine, methyldopa, rilmenidine.

#### Authorized treatments:

Patients treated with antihypertensive drugs such as diuretics, angiotensin converting enzyme (ACE) inhibitors, angiotensin receptor blockers (ARBs), or calcium blockers (dihydropyridines only) can continue their treatment at a stable dose during the whole study, with maximum of a dual combination of 2 antihypertensive drugs, and if the patient has stable blood pressure.

Patients treated for depression and stabilized with non IMAO (inhibitors of MAO) antidepressants can continue their treatment at stable dose during the whole study. Allowed antidepressants are:

- SSRIs (selective serotonin reuptake inhibitors): fluoxetine, paroxetine (see precautions below), citalopram, sertraline.
- SNRIs (serotonin-noradrenaline reuptake inhibitors): duloxetine, venlafaxine.
- TCAs (tricyclic antidepressants): amitriptyline, clomipramine, imipramine, nortriptyline, lofepramine.

Neuroleptics treatment (excluding haloperidol, pimozide, and tiapride), if needed to treat a behavior disorder and prescribed for at least 3 months at a stable dose, can be maintained at a stable dose during the whole study, provided that it is approved on a case-by-case basis by the Steering Committee before enrolment of the patient.

Treatments to be used with precautions (because of risk of interactions):

- Alpha-blockers.
- Local beta-blockers (eye drop) or pilocarpine (eye drop).
- Anticholinesterase drugs: donepezil, rivastigmine.
- Strong CYP2D6 inhibitors may increase the blood levels of SOM3355 (such as paroxetine fluoxetine, quinidine, bupropion, dacomitinib, tipranavir).

# Investigational treatments

The study medication will be provided in capsules of SOM3355 dosed at 200 mg or 300 mg, or matching placebo. SOM3355 capsules will contain 2 or 3 tablets of 100 mg of the commercial form of bevantolol (Calvan® 100 mg tablets). The capsules will be identical in appearance to ensure that neither the patient nor the Investigator or the clinical staff know the exact nature of the study medication.

Patients should take 1 capsule in the morning during the first week and then 1 capsule twice per day, one in the morning and one in the evening (every 12 hours) during the following 9 weeks, and then only 1 capsule in the morning during the last 2 weeks. Capsules can be taken with food.

At the inclusion visit (Day 0), patients will be allocated according to the randomization list to one of the 3 treatment arms, starting with 3 weeks of up-titration, to receive either SOM3355 400 mg/day, SOM3355 600 mg/day, or placebo for up to 10 weeks. This will be followed by 1 week of down titration and 1 week of placebo wash-out period to assess the effect of drug interruption.

The total treatment duration of this double-blind study, from the inclusion visit, will be 12 weeks (+ 1 or 2 weeks for screening before inclusion): 11 weeks under the active drug treatment (or placebo), and 1 week under placebo for all patients at the end of the study.

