	A first proof-of-concept (PoC) Phase IIa trial was conducted in 32 HD patients to test the efficacy and safety of SOM3355 100 and 200 mg BID doses compared to placebo. This provided confirmation of the expected effects of SOM3355 on the chorea symptoms measured by the Total Maximal Chorea (TMC) score, which significantly improved while patients were receiving 200 mg BID SOM3355 in comparison to placebo. SOM3355 was well-tolerated, with no concern about depression or suicidality risk, and the most frequent treatment emergent adverse events, all mild or moderate, being bradycardia, hypotension, insomnia, and falls, which were expected and explained by the known effects of the drug.  Following the results of the first PoC and the PK-PD assessment indicating that higher doses may be more efficacious, this Phase IIb study will be conducted.
Objectives	The primary objective of the study is to assess the efficacy of two doses of SOM3355 (400 mg/day and 600 mg/day taken twice daily [BID] over at least 8 weeks at maintenance dose) compared to placebo to reduce chorea in HD patients measured by the change in TMC score (primary efficacy endpoint). Secondary objectives of the study are:  To evaluate the safety and tolerability of two doses of SOM3355 (400 mg/day and 600 mg/day taken) compared with placebo in HD patients, with particular attention to depression and suicidality and to the cardiovascular hemodynamic parameters.
	And to evaluate the efficacy of the two doses of SOM3355 (400 mg/day and 600 mg/day taken BID) compared with placebo on:  the change of Clinical Global Impression (CGI-C), the change of Patient Global Impression (PGI-C), the percentage of responders based on the improvement ≥2 in TMC score, the percentage of change of TMC score.  A pharmacokinetic (PK) sub-study in a subset of 24 patients will allow to determine the PK profile of the two doses of SOM3355 (200 mg and 300 mg given twice per day) at steady state and to model PK-PD assessments of hemodynamic and cardiac parameters.
Study design	This is an international, multicenter, double-blind, randomized, placebo-controlled, parallel-group Phase IIb study assessing two doses of SOM3355 (400 or 600 mg/day), taken as 200 mg BID or 300 mg BID, in patients presenting choreic symptoms related to HD.

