# Sample size and statistical methodology

#### Sample size calculation

The sample size requires enrollment of a total of 129 patients in the randomized treatment period, allowing for a drop-out rate of 10%. Eligible patients will be randomized in blinded fashion in a 1:1:1 ratio i.e. 43 patients in each arm (SOM3355 400 mg/day, SOM3355 600 mg/day, or placebo). Assuming a treatment difference of -2.5 points in the change from baseline of TMC score compared to placebo and a standard deviation of 3.5, 39 patients per arm are needed to provide at least 80% power that at least 1 dose of SOM3355 will be significantly superior to placebo at the 2-sided 0.025 significance level. This is based on the use of a two-sided t-test for the mean TMC score change. With a dropout rate of approximately 10%, 43 patients per arm have to be enrolled i.e. a total of 129 patients. If the dropout rate is higher than 10%, then an upward adjustment of sample size might be considered.

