## 7.3.3. Vital signs (Heart rate and Blood Pressure)

Blood pressure and heart rate must be measured in clinic at the beginning of each visit (before ECGs and/or blood sample collection) according to the European Society of Hypertension guidelines (Stergiou et al. 2021 ESH guidelines). Standardization for blood pressure measurements is necessary to obtain consistency of the collected data. Vital signs should be measured at each visit in the same conditions, with a validated and calibrated electronic device and using an adequate cuff for the arm circumference of the patient. The electronic device to be used for blood pressure measurement must be listed among the validated devices in the: https://www.stridebp.org website.

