# 7.5.2. Prolactin plasma level

An increase in prolactin plasma levels was observed with SOM3355 administration in the previous Phase 2a POC study, consistent with that seen with other VMAT2 inhibitors like tetrabenazine. However, the increase was found not to be dose-proportional with SOM3355 levels, showing a mean increase of 1.7- and 1.9-fold at the 100 mg and 200 mg BID doses, respectively (SOMCT02 – PK/PD Report). This may reflect changes in dopaminergic tone in the hypothalamus and/or pituitary gland (Orrillo et al, 2020). Therefore, prolactin plasma levels could be considered as a biomarker of the pharmacodynamic (PD) effect of SOM3355.

Blood samples will be obtained at each visit from Visit 1 to Visit 6 in all patients to measure prolactin plasma concentration, before dosing at each visit and 2 hours after dosing at Visit 2 and Visit 4. Prolactin plasma quantification will be determined by chemiluminescence technique.

Samples will be collected and stored with the PK samples and analyzed by the central laboratory in order to keep the blind during the study.

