# 8.1.5. Visit 4 - Week 9 - Day 63 - 1st assessment at end of maintenance dose

At Visit 4, the Investigator must perform the following assessments:

- Physical and neurological examinations;
- Vital signs (SBP and DBP, orthostatic BP, and HR);
- Clinical scores and functional tests: UHDRS®-Motor part only, C-SSRS, BDI, ESS, CGI-C and PGI-C;
- 12-lead ECG (sent for centralized reading by a cardiologist) at Tmax (2 hours after dosing) just before the blood sample;
- Blood sample for PK and prolactin level (central lab) at pre-dose and 2 hours after dosing;
- List of current concomitant medications;
- Recording of AEs;
- Drug accountability of the returned study medication and review of compliance (the patient is asked whether the investigational treatment was taken as prescribed or any incidents occurred to double-check with the returned Patient Diary);

- Drug dispensation: the patient will receive 2 bottles of study medication and a new Patient Diary and will be instructed to take two capsules per day, one in the morning and one in the evening until the next visit and record the intakes in the Diary. The first dose will be administered to the patient during the visit. The patient will be instructed to contact the Investigator by phone should an AE occur, and will be asked to bring back the used and unused bottles of study medication at the following visit. An Extra bottle is provided in case of delayed visit to avoid an interruption of the study treatment;
- The patient is asked to come at the next visit without taking the morning dose to enable the blood sampling for PK at trough.

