## 9.3. SAMPLE SIZE DETERMINATION

The sample size will be a total of **129 patients**. Eligible patients will be randomized in blinded fashion in a **1:1:1 ratio** i.e. **43 patients in each arm** (SOM3355 400 mg/day, SOM3355 600 mg/day, or placebo). Assuming a treatment difference of -2.5 points in the change from baseline of TMC score compared to placebo and a standard deviation of 3.5, 39 patients per arm will provide at least 80% power that at least 1 dose of SOM3355 will be significantly superior to placebo at the 2-sided 0.025

significance level. For the primary endpoint, the overall type I error will be controlled using a Holm procedure. To account for a 10% dropout rate, 43 patients per arm (i.e. a total of 129 patients) will be enrolled.

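### Nothing keeps the rater of TMC and CGI-C from seeing heart rate and blood pressure first, so a β1-blocker can hint at active versus placebo before the primary endpoint is scored

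*Protocol*

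**What the plan says.** **Stated basis of the blind.** The synopsis (Investigational treatments) says: "The capsules will be identical in appearance to ensure that neither the patient nor the Investigator or the clinical staff know the exact nature" of what is given. Section 6.1 repeats this for the matching placebo.

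**Visible drug effects.** The synopsis describes the most frequent adverse events of the Phase IIa trial as "being bradycardia, hypotension, insomnia, and falls, which were expected and explained by the known effects of the drug". Sections 2.1.6.1 and 2.2.1 attribute bradycardia and hypotension to β1-blockade. Section 2.2.1 calls the resting heart-rate effect mild and gives no bpm figure.

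**Timing of vital signs.** Section 7.3.3: "Blood pressure and heart rate must be measured in clinic at the beginning of each visit (before ECGs and/or blood sample collection". Readings are taken sitting, supine and standing, and the patient is asked about light-headedness or dizziness.

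**Who does what.** Sections 8.1.3 to 8.1.7 each give one list under one responsible role, for example "At Visit 4, the Investigator must perform the following assessments". The list covers vital signs, the UHDRS motor part (which contains TMC), CGI-C and AE recording. Section 8 has visits conducted by investigators and sub-investigators; no separate efficacy rater is required.

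**Other cues.** Section 7.3.4 lets the Investigator read a paper ECG during the visit. At Visit 4, one of the two primary-endpoint visits, the ECG is taken 2 hours after dosing (8.1.5). Section 5.7 lists hypotension, orthostatic hypotension and bradycardia among the grounds for withdrawal, so the Investigator has reason to look at these values.

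**Protection given elsewhere.** Prolactin samples are "analyzed by the central laboratory in order to keep the blind during the study" (7.5.2), and PK sub-study results stay blinded until data lock (4.2).

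**The concern.** TMC is a clinician's sum of seven 0-to-4 ratings, and CGI-C is a clinician's impression of change. Both can move with what the rater expects. SAP 2.2 and 4.7.2 also bring CGI-C under multiplicity control as the key secondary endpoint, so two confirmatory tests rest on the same kind of rating.

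The plan accepts that a drug effect can break the blind, because it sends prolactin to a central laboratory for that reason. The effect that can be seen at the bedside has no such protection. If raters score patients they believe to be on drug a little lower, the shift enters the drug-placebo difference directly. The MMRM cannot separate it from efficacy. The four sensitivity analyses in SAP 4.7.1 (reference-based imputation, observed-case ANCOVA, per-protocol, and no imputation for discontinued patients) address missing data and deviations, not rating bias.

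**Working it through.** **1. The plan's own figure.** The inputs come from protocol 9.3 and the sample-size part of the synopsis.

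- Effect and SD (9.3): "Assuming a treatment difference of -2.5 points in the change from baseline of TMC score compared to placebo and a standard deviation of 3.5".
- Size and power target, as worded in the synopsis: "39 patients per arm are needed to provide at least 80% power that at least 1 dose".
- Level for the first Holm step, also from the synopsis: "significantly superior to placebo at the 2-sided 0.025 significance level".
- Normal approximation: n = 2(2.241 + 0.842)² × 3.5² / 2.5² = 37.3, so 38 per arm.
- Noncentral t: power 0.794 at 38 and 0.805 at 39, so the stated 39 per arm reproduces. The sample size is not in dispute; it supplies the scale for what follows.
- Standard error of a dose-placebo difference: 3.5 × √(2/39) = 0.793 points. The critical t (76 df, upper tail 0.0125) is 2.287, so the smallest significant difference is 2.287 × 0.793 = 1.81 points.

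**2. How much a heart-rate reading tells the rater.** The documents give no bpm effect and no SD. Assumptions: fall δ = 3, 5 or 8 bpm; between-patient SD of change σ = 7 or 9 bpm; one reading. Allocation is 1:1:1, so two thirds of patients are on active drug. A rater making the best use of one reading guesses active when the likelihood ratio exceeds 1/2, which gives

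- P(guess active, on active) = Φ(δ/2σ + σ ln 2/δ)
- P(guess active, on placebo) = Φ(−δ/2σ + σ ln 2/δ)

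The gap between the two drives the bias. With an assumed rater shift g of 1 to 2 TMC points toward supposed-active patients, bias = g × gap.

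| δ (bpm) | σ (bpm) | on active | on placebo | gap | bias, g = 1 to 2 |
|---|---|---|---|---|---|
| 3 | 9 | 0.99 | 0.97 | 0.02 | 0.02 to 0.03 |
| 3 | 7 | 0.97 | 0.92 | 0.05 | 0.05 to 0.09 |
| 5 | 9 | 0.94 | 0.83 | 0.10 | 0.10 to 0.20 |
| 5 | 7 | 0.91 | 0.73 | 0.18 | 0.18 to 0.36 |
| 8 | 9 | 0.89 | 0.63 | 0.26 | 0.26 to 0.52 |
| 8 | 7 | 0.88 | 0.51 | 0.37 | 0.37 to 0.73 |

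The range is about 0.02 to 0.7 points.

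**3. What such a bias does to the test.** With no true effect and bias b, the noncentrality is b/0.793. The false-superiority rate per dose is the upper tail beyond 2.287 on 76 df:

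| b (points) | b/0.793 | false superiority per dose |
|---|---|---|
| 0 | 0 | 1.25% |
| 0.02 | 0.03 | 1.3% |
| 0.3 | 0.38 | 3.1% |
| 0.5 | 0.63 | 5.3% |
| 0.73 | 0.92 | 9.1% |

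Counting a false success on at least one dose (simulation of three arms of 39, SD 3.5, smaller p-value below 0.025 in favour of active), the rate is 2.3% with no bias, 4.9% at 0.25 points and 9.2% at 0.5 points.

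**The case against.** **The visit lists set no sequence.** A reader might infer from 8.1.3 to 8.1.7 that vital signs must be done before the scores. The lists cannot be read that way: at Visits 2 and 4 the 2-hour post-dose sample stands above the item in which the dose is given. The only order that 7.3.3 spells out is relative to ECG and blood sampling. This stands. The point rests on the start-of-visit wording in 7.3.3 and on the absence of any rule that rating comes first.

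**No passage requires one person to do both.** A reader might infer that the rater must take the readings personally. The same lists include self-report scales and blood draws, so they assign responsibility rather than one pair of hands, and a site may use two sub-investigators. This also stands: separation is allowed, but nothing requires it.

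**The cue is weak.** Patients are asked to arrive without the morning dose at the treatment visits, so readings at the start of those visits are near trough, and the resting effect is called mild. That supports a modest assumed fall, not zero. Dizziness questions, AE recording and the post-dose Visit 4 ECG can add to it.

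**Raters might be thought to guess far better than chance.** With even odds, Φ(δ/2σ) gives 57% to 72% correct and a gap of 13 to 43 percentage points. The plan's allocation does not support even odds: always guessing active is right 67% of the time with no information. With the 2:1 split the gap is about 2 to 37 points.

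**Reordering hides only that day's reading.** By Visits 4 and 5 a sole Investigator has seen earlier values. This stands and limits what the fix can do.

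**Conclusion.** The concern holds as a gap in rater masking. The blind is attributed to identical capsules, vital signs open every visit, and neither document keeps them from the rater of a subjective primary endpoint. What the rater may gain is a probabilistic hint of active versus placebo.

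A reader might infer that the readings reveal the arm or separate 400 from 600 mg/day. Nothing in the documents shows that. Nor do they show that any bias will occur.

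The bias range of about 0.02 to 0.7 TMC points rests entirely on assumed values for the heart-rate fall, its SD and the rater shift, together with the plan's own allocation. At the low end the effect on the error rate is negligible (1.25% to 1.3% per dose). At 0.3 or 0.5 points it is about 3% or 5%. With the size unknown and a remedy that needs no new staff, the change should be made.

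**What to change.** Amend protocol 7.3.3 and 8.1.1 to 8.1.7 as follows.

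1. **Order, at all visits V0 to V6.** Complete and save the UHDRS motor part, and the CGI and PGI where scheduled, before vital signs, AE questioning and ECG. Then take vital signs after the rests already required, still before dosing and blood sampling where these apply. V0 and V1 must be included: SAP 4.1.1 takes the vital-sign baseline at V1, and 7.3.3 asks for the same conditions at each visit. Changing only V2 to V6 would compare readings taken after the motor examination with a baseline taken before it.
2. **Access.** State that the rater does not consult heart-rate, BP, ECG or AE data from that visit or earlier ones before saving the rating.
3. **People.** Where a site already has two qualified investigators or sub-investigators, assign the rating and the safety review to different people.
4. **Optional.** Record the rater's guessed arm at V5 and tabulate it by arm. Treat this as descriptive only, since guesses also reflect perceived efficacy.

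**Cost.** Protocol wording and a changed order of existing procedures, plus one eCRF item and one table if the guess is collected. Doses, withdrawal criteria, sample size and the primary model are untouched.

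**Downsides.** Vital signs will follow the motor examination at every visit. The rating is fixed as pre-dose at dosing visits, a timing that the protocol now leaves open. A sole Investigator still remembers earlier values, so the risk is reduced, not removed.

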# Primary efficacy endpoint

The primary measure of efficacy will be the change in Total Maximal Chorea (TMC) sub-score of the Unified Huntington's Disease Rating Scale (UHDRS®) between baseline and end of maintenance dose (the mean of Visit 4 and Visit 5 minus the mean of Visit 0 and Visit 1).

The TMC score is a standardized, reliable chorea assessment based on frequency and severity in 7 body regions.

# Secondary efficacy endpoints

Key secondary efficacy endpoint:

• Change from baseline in the Clinical Global Impression (CGI-C).

Other secondary efficacy endpoints:

- Change from baseline in the Patient Global Impression (PGI-C).
- TMC-response defined as improvement ≥2 in TMC score between baseline and end of maintenance dose.
- Percentage of change in TMC score between baseline and the end of maintenance dose.
- Change from baseline in Total Motor Score (TMS) of the UHDRS®.
- Change from baseline in Gait sub-score of the UHDRS®.
- Change from baseline in Dystonia sub-score of the UHDRS®.
- Change from baseline in EQ5D-5L measuring quality of life.

#### Safety endpoints

Safety assessments will include the following:

- Incidence, frequency, and severity of adverse events (AEs) in each treatment group.
- Change from baseline in:
  - Vital signs: blood pressure (BP), including orthostatic BP, and heart rate (HR).

	
 
ECGs.
 
Clinical laboratory test results (chemistry, hematology).
 
Physical examination findings, weight.
 
Columbia-Suicide Severity Rating Scale (C-SSRS) assessing suicidality.
 
Beck Depression Inventory (BDI) scale assessing depression.
 
Epworth Sleepiness Scale (ESS) assessing sleepiness.
 
Total Functional Capacity (TFC) of the UHDRS® assessing functioning.
 
Functional Assessment of the UHDRS®.
 
					
	
 
Barnes Akathisia Rating Scale (BARS) assessing akathisia.
 
Montreal Cognitive Assessment (MoCA) scale to assess cognitive disturbances.
 
					
	Problem Behaviors Assessment short form (PBA-s) to assess behavioral symptoms in HD.					
PK-PD assessments	SOM3355 plasma concentration will be measured at each visit under treatment with SOM3355 (i.e. from Visit 2 to Visit 5) in all patients. Plasma samples will be collected pre-dose (before the dug intake) and 2 hours after the drug intake (corresponding to the expected $T_{max}$ ) at Visit 2 and Visit 4, and only pre-dose at Visit 3 and Visit 5.					
	Prolactin plasma level will be measured at each visit from Visit 1 to Visit 6 in all patients. Plasma samples will be collected pre-dose (before the dug intake) and 2 hours after the drug intake (at T max ) at Visit 2 and Visit 4, and only pre-dose at Visit 1, Visit 3, Visit 5, and Visit 6.					
PK sub-study	A PK sub-study will be conducted to characterize the PK profile of repeated doses of SOM3355 at 400 and 600 mg/day. This analysis will be performed by collecting 12-hour PK samples (H0, H0.5, H1, H1.5, H2, H3, H5, H8, and H12) in 8 patients per arm (24 patients in total) that will be hospitalized for 24 hours at Visit 2. In addition, cardiac and hemodynamic parameters will be collected in parallel, with 12-hour cardiac Holter and blood pressure measurements before each PK sample, to allow PK-PD modeling assessments. These patients will be recruited by 3 or 4 sites able to manage the logistics of PK sampling.					

